## 13.0 STATISTICAL ANALYSIS

### 13.1 Sample Size Determination

Prior study data was used to estimate the expected mean change (28.5) and standard deviation (30.3) for the change in NOSE score from baseline to 6 months (26 weeks). N=45 subjects would provide 90% power to test the study hypothesis at the one-sided alpha level of 0.05. To allow for up to 10% attrition, a total of 50 subjects will be enrolled.

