### 13.4 Primary Endpoint – Efficacy Analysis

The study hypothesis will be tested by calculating the change in NOSE scores from baseline to 26 weeks (baseline – 26 weeks). The lower limit of the one-sided 95% confidence interval will be calculated using the t-distribution. Should the lower limit exceed 15.0, then the null hypothesis will be rejected in favor of the alternative.

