### 13.8.2 Handling Dropouts, Loss-to-Follow-up or Missing Data

All efforts will be made to collect all data points in this study. The study hypothesis will be tested using all available data for the subjects in the efficacy patient population. If the primary endpoint is not available for all such subjects, then additional analyses will be performed in order to assess the potential effect of missing data on the study conclusions. First an analysis will be performed, treating all missing data points for the primary endpoint as 0 improvement. If the study conclusion is upheld using this type of worst-case scenario, no other analyses will be performed. Otherwise, a multiple imputation approach will be used. The propensity method will be used including the baseline, 4 week and 12 week NOSE scores if they are available. Fifteen imputed datasets will be generated and the study hypothesis will be repeated on the imputed dataset to determine if the study hypothesis is upheld.

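### Propensity-method imputation uses the week-4 and week-12 NOSE scores only to model who is missing; regression imputation on the same data would be a slightly more accurate final missing-data check (minor)

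*Combined protocol and SAP*

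**What the plan says.** Section 13.4 sets the primary test on improvement, defined as baseline minus week 26. "The lower limit of the one-sided 95% confidence interval will be calculated using the t-distribution", and "Should the lower limit exceed 15.0, then the null hypothesis will be rejected in favor of the alternative".

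Section 13.8.2 then handles missing week-26 data in three steps.

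1. The primary result uses observed data: "The study hypothesis will be tested using all available data for the subjects in the efficacy patient population". That population is not defined under this name; I read it as the evaluable subjects of section 13.3.
2. If any primary endpoint value is missing, it is set to zero improvement. If the conclusion holds, the analysis stops there.
3. Otherwise multiple imputation is used: "The propensity method will be used including the baseline, 4 week and 12 week NOSE scores if they are available". On the number of sets and the test, the plan says: "Fifteen imputed datasets will be generated and the study hypothesis will be repeated on the imputed dataset".

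The section does not define the propensity model, the number of groups, the variable imputed (week-26 score or change), the handling of subjects without a week-4 or week-12 score, or a rule for combining the 15 results. Section 13.1 plans for the loss: "To allow for up to 10% attrition, a total of 50 subjects will be enrolled". The documents give no between-visit correlation and no expected dropout mechanism.

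**The concern.** The usual propensity method fits a logistic model for being missing, sorts subjects into groups by the fitted score, and fills each gap with a value resampled from observed subjects in the same group. The week-4 and week-12 scores enter only through that fitted score. How closely a subject's own week-12 result predicts the week-26 result is not used.

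With few missing subjects the missingness model is poorly estimated, so the groups are partly noise. Subjects who did badly at week 12 can then receive values from donors who did better. If such subjects are the ones lost, the imputed mean improvement is pulled upward.

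The step is a sensitivity analysis, but it is the last one in the sequence. It runs only when the zero-improvement analysis has not upheld the conclusion, so its result settles whether the finding is reported as robust to dropout.

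**Working it through.** **The plan's own figure.** Section 13.1 gives a mean change of 28.5 and SD of 30.3, tested against 15 at one-sided 0.05. The difference is 28.5 − 15 = 13.5. With the noncentral t distribution, the smallest N with at least 90% power is 45 (power 0.903), and 45 / 0.90 = 50. The plan's statement that "N=45 subjects would provide 90% power to test the study hypothesis at the one-sided alpha level of 0.05" is reproduced.

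**Scale.**
- Standard error of the mean change: 30.3 / √45 = 4.52 with 45 subjects; 30.3 / √50 = 4.29 with 50.
- Expected missing: 50 × 0.10 = 5 subjects. Events per predictor: 5 / 3 = 1.7.

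**Simulation inputs.** From the documents: n = 50, SD 30.3, true mean 15 (the null value), 15 imputations, and baseline, week 4 and week 12 as predictors. Assumed, because the documents are silent:
- correlation between visit improvements of 0.5, 0.7 or 0.85;
- log-odds of losing week 26 rising by 1 or 2 per SD of poorer week-12 improvement;
- five propensity groups with an approximate Bayesian bootstrap;
- normal, unbounded scores, with weeks 4 and 12 always observed.

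The comparator is Bayesian linear regression on the same three scores. Both methods are pooled by Rubin's rules: Q̄ = mean of the 15 estimates, T = W + (1 + 1/15)B, lower limit = Q̄ − t(0.95, ν)√T with small-sample ν. There were 1,500 trials per setting. Monte Carlo SE is about 0.03 to 0.08 points for bias and 0.6 to 0.8 percentage points for error rates.

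**Results at 10% missing.** Bias is in NOSE points against the full-data mean; error is stand-alone, one-sided.

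| Correlation | Log-odds | Available-case bias | Propensity bias | Regression bias | Propensity error | Regression error |
|---|---|---|---|---|---|---|
| 0.5 | 1 | +1.40 | +0.24 | −0.03 | 5.3% | 4.7% |
| 0.5 | 2 | +2.14 | +0.49 | +0.03 | 6.3% | 5.2% |
| 0.7 | 1 | +1.99 | +0.32 | −0.02 | 6.3% | 5.5% |
| 0.7 | 2 | +3.09 | +0.67 | +0.02 | 7.3% | 5.4% |
| 0.85 | 1 | +2.40 | +0.38 | −0.02 | 5.3% | 4.1% |
| 0.85 | 2 | +3.69 | +0.78 | +0.01 | 7.9% | 4.7% |

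The largest propensity bias is 0.78 / 4.52 = 0.17 of a standard error. Over all runs made for this point, with slightly different settings, stand-alone error at 10% missing is about 5 to 8% for propensity and 4 to 6.5% for regression. At 20% missing, propensity bias is +0.41 to +1.15 with error of 6.3 to 10.3%; regression gives −0.12 to +0.03 and 4.6 to 6.3%.

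**Accuracy.** At correlation 0.7, 10% missing and log-odds 1.0 to 1.5, root-mean-square error against the full-data mean is 1.3 to 1.5 points for propensity and about 1.1 for regression. Under random loss it is 1.14 against 1.00.

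**Other dropout mechanisms (10% missing unless stated).**
- Random loss: bias +0.04 (propensity) and +0.03 (regression).
- Good responders lost: the propensity bias reverses, to −0.31.
- Loss depending on the week-26 value itself: propensity +1.4 to +2.0, regression +1.15 to +1.9. In a strong case at 20% missing: +4.6 and +4.0.

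**Full sequence (true mean 15, correlation 0.7).** This runs available cases, then zero improvement, then imputation. The final upheld rate at 10% missing is 7.3% with propensity against 6.9% with regression (log-odds 1.0), and 7.2% against 6.6% (log-odds 1.5). The choice of method changes the conclusion in about 0.6 to 0.7% of trials. At 20% missing it is 9.0% against 7.3%, a gap of 1.7 points.

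A separate set of 3,000 trials per setting agrees. At log-odds 1.0, imputation was triggered in 162 (5.4%) and upheld a false success in 25% of these with propensity and 17% with regression: 0.054 × 0.08 = 0.4 points. At log-odds 1.5, it was triggered in 203 (6.8%), with 15% against 6%: 0.068 × 0.09 = 0.6 points.

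**Power.** At the planned mean of 28.5 and 10% missing, stand-alone rejection is 0.922 (propensity) and 0.920 (regression).

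**The case against.** The strongest defence is that this is a conditional sensitivity analysis that already does most of its job. Success under section 13.4 rests on available data. In the runs where poor responders leave, the propensity step removes 77 to 87% of the available-case bias; in the first row of the table, for example, 1 − 0.24/1.40 = 83%. The larger bias sits in the available-case test, which a change of imputation method does not touch. This stands, and it is why the point is minor.

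The simulation also favours regression somewhat. Its scores are linear and normal and its earlier visits complete, whereas section 13.8.2 foresees that some may be unavailable. A subject lost before week 12 gains less from regression. This stands too. Still, no setting tested showed a material advantage for the propensity method.

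Four stronger readings are tempting, and the documents do not support them.

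- A reader might infer that the method is biased toward success in general. That requires poor responders to be the ones lost, and the documents state no dropout mechanism.
- A reader might infer that regression with pooled limits removes the bias. It does so only when loss depends on observed scores, and pooling corrects the variance, not the bias.
- A reader might infer from the singular noun for the imputed dataset that the 15 sets would be stacked and tested once. That would shrink the standard error to 30.3 / √750 = 1.1 and give false success of roughly 35 to 45% in simulation. But the same sentence specifies fifteen datasets, the one before it names multiple imputation, and nothing says to stack them. The gap is a missing combining rule.
- A reader might infer that a subject's own baseline is ignored in the imputed improvement. The plan does not say whether the score or the change is imputed; if it is the change, that criticism fails.

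**Conclusion.** The point holds as a minor, free improvement. In its usual form the named method makes less use of the early NOSE scores than regression does, so the final missing-data check is less accurate. That loss of accuracy appears even under random loss.

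The error favours success only if poor week-12 responders leave. Even then it is under a fifth of a standard error at the planned attrition and rarely alters the sequence's outcome. These sizes rest on the assumed correlations, the assumed dropout model and the five-group form of the method. The primary test and the sample size are not affected.

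The absent combining rule is a separate gap in specification: section 13.4 needs one lower limit, and section 13.8.2 does not say how fifteen results produce it.

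**What to change.** In section 13.8.2:

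1. Replace the propensity method with regression or predictive-mean-matching multiple imputation of the week-26 NOSE score from the baseline, week-4 and week-12 scores. Fill missing earlier visits sequentially, and compute improvement (baseline minus week 26) within each completed dataset.
2. Separately, state that the 15 estimates and variances are combined by Rubin's rules into one pooled one-sided 95% lower limit, which is compared with 15.0.

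Neither change protects against loss that depends on the unseen week-26 score. A shift (delta) sensitivity analysis could be added for that.

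The cost of the two changes is SAP wording only. NOSE is already collected at all the visits needed (Table 1), and sample size and visits stay as they are.

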### 13.8.3 Multicenter Study

Data from up to 10 investigational sites will be pooled for this study. The justification for pooling is made on a clinical basis (Meinert and Tonascia 1986). This study will be conducted such that: 1) the same protocol will be used at each site; 2) site investigators and personnel will receive uniform training; and 3) central data management and monitoring will be consistent and applied with equal rigor at all sites. The diversity of hospital and clinical practice settings will add to the scientific validity and generalizability of the findings.

An analysis of the consistency of the “treatment effect” across sites cannot be made directly in this study since it is a single arm study. Observed differences across sites could be due to differences in patient populations or in the performance of the device. The primary endpoint results will be stratified by clinical center. If any sites have fewer than 5 subjects in the analysis group, they will be pooled together (if there are more than one), or with the next smallest site if there is only one. The mean changes in NOSE score will be compared statistically using analysis of variance. The p-value for statistically significant differences across sites will be set at the 0.15 level.

Demographics and baseline characteristics will also be stratified by site. Should the comparison in mean change for the primary endpoint result in a significant difference across sites, then the demographics and baseline characteristics will also be compared statistically across sites. Fisher’s Exact test will be used for categorical outcomes, and analysis of variance for continuous outcomes. Any characteristics found to be statistically significant at the 0.15 level will be included in the model comparing the primary endpoint outcome across sites. A generalized linear model will be used with change in NOSE score playing the role of the

dependent variable and site and statistically significant characteristics as independent variables. The differences in outcome across sites, after adjusting for differences in baseline characteristics will be assessed. A p-value > 0.15 will indicate no significant differences across sites.

#### 14.0 SAFETY RELATED STOPPING RULES

The study sponsor will be charged with monitoring the study for safety and for auditing the quality of the data. If there are any perceived safety concerns related to the Vivaer™ System or procedure, the trial may be terminated.

#### 15.0 QUALITY ASSURANCE AND SUPERVISION BY AUTHORITIES

This study will be conducted in accordance with elements of E6 Good Clinical Practice Consolidated Guidance, ICH, April 1996, abbreviated requirements of 21 CFR 812.2(b) for Non-significant Risk (NSR) device studies, the Declaration of Helsinki, the Belmont Report, and IRB/EC requirements.

All documents and data shall be produced and maintained in such a way to assure control of documents and data to protect the patient's privacy as far as reasonably practicable. The Sponsor and representatives of the FDA or other regulatory authorities are permitted to inspect the study documents (e.g., study protocol, CRFs, and original study-relevant medical records/files) as needed. All attempts will be made to preserve patient confidentiality.

All clinical sites are subject to audit by study sponsor personnel or designee for protocol adherence, accuracy of CRFs and compliance with applicable regulations. Any evident pattern of non-compliance with respect to these standards will be cause for corrective action.

The study protocol, data-recording procedures, data handling as well as study reports are subject to an independent clinical Quality Assurance audit by the study sponsor, its designee, or health authorities.

#### 16.0 STUDY MANAGEMENT

This study will be conducted in accordance with elements of E6 Good Clinical Practice Consolidated Guidance, ICH, April 1996, Abbreviated Requirements of 21 CFR 812 for NSR device studies, the Declaration of Helsinki, the Belmont Report and any conditions imposed by the reviewing IRB or US FDA or other regulatory agency.

The study sponsor has the overall responsibility for the conduct of the study according to all applicable regulatory requirements. The study sponsor will have certain direct responsibilities and will delegate other responsibilities to the Principal Investigator. The study sponsor and Principal Investigator will ensure that the study is conducted according to all applicable regulations. All personnel to participate in the conduct of this clinical trial will be qualified by education and / or experience to perform their tasks.

The study sponsor, Investigator or any person acting for or on behalf of a sponsor or Investigator shall act in accordance the applicable standards, guidelines and regulations.

## 17.0 INVESTIGATIONAL DEVICE MANAGEMENT

The Vivaer™ System is investigational and is not approved for commercial use in the United States. The investigator shall maintain adequate records of the receipt and disposition of all investigational devices. When trial enrollment is complete, the investigator shall return any unused devices to the sponsor or their designee. The device will only be used as part of this clinical trial in eligible patients and will be used according to its intended use. A copy of the Instructions for Use (IFU) accompanies each study device.

## 18.0 REQUIRED DOCUMENTS FROM THE INVESTIGATOR (PRIOR TO STUDY START)

At a minimum, the following documents will be provided by the investigational site to the study sponsor:

- Signed Investigator Agreement
- Signed Clinical Investigational Plan (CIP) Signature Page
- IRB/EC approval
- IRB/EC approved Informed Consent Form (ICF)
- Investigator and Co-Investigator's current Curriculum Vitae
- Investigator and Co-Investigator's current Medical Licenses

A site may not begin study participation until all of the above listed documents have been provided to the study sponsor.

## 19.0 TRAINING

The Vivaer™ System is intended for use by experienced medical personnel. The Investigator will be provided training by the study sponsor in the use of the device to familiarize them with the use of the Vivaer System prior to their participation in the clinical study.

Each study center will undergo protocol initiation including but not limited to a review of the following:

- Procedures for obtaining Informed Consent
- Procedures for completing Informed Consent Form
- Device usage instructions
- Reporting requirements
- CRF completion and correction procedures
- Vivaer System overview
- Protection of patient confidentiality

## 20.0 ETHICAL CONSIDERATIONS

The rights, safety and wellbeing of clinical investigation subjects shall be protected consistent with the ethical principles outlined in the Declaration of Helsinki. This shall be understood, observed and applied at every step in this clinical investigation.

It is expected that all parties will share in the responsibility for ethical conduct in accordance with their respective roles in the investigation. The Sponsor and the Investigator shall avoid improper influence or inducement of the patient, study monitor, clinical investigator or other parties participating in or contributing to the clinical investigation.

## 21.0 PROTECTION OF PATIENT CONFIDENTIALITY

At all times throughout the clinical investigation, confidentiality will be observed by all parties involved. All data shall be secured against unauthorized access. Privacy and confidentiality of information about each patient shall be preserved in the reports and in any publication. Each patient participating in this study will be assigned a unique identifier. All CRFs will be tracked, evaluated, and stored using only this unique identifier.

The investigational site will maintain a confidential study patient list (paper or electronic) identifying all enrolled patients. This list will contain the assigned study patient's unique identifier and name. The Site Principal Investigator (PI) bears responsibility for keeping this list confidential. This list will not be provided to the study sponsor and is only to be used at the study center.

Monitors and auditors will have access to the study patient list and other personally identifying information of study patients to ensure that data reported in the CRF corresponds to the person who signed the ICF and the information contained in the original source documents. Such personal identifying information may include, but is not limited to the patient's name, address, date of birth, gender, race and medical record number.

*NOTE: The patient's name, medical record number or address will NOT be recorded in the monitor's visit report or the database; demographic data that may be recorded includes age, race, and gender.*

Any source documents copied for monitoring purposes by the Sponsor will have patient identifiable information redacted and be identified by using the assigned patient's unique identifier in an effort to protect patient confidentiality.

## 22.0 DATA COLLECTION

Study data will be collected using standardized Case Report Forms (CRFs). The CRFs are designed to accommodate the specific features of the trial design. Modification of CRFs will only be made if deemed necessary by the study sponsor.

## 23.0 SOURCE DATA VERIFICATION

At a minimum, source data verification will be performed on all primary endpoint, secondary endpoint and safety data for each patient enrolled in this study.

## 24.0 STUDY SUSPENSION OR EARLY TERMINATION

The study can be discontinued at the discretion of the Site PI or Sponsor for reasons including, but not limited to, the following:

- Occurrence of adverse events unknown to date in respect to their nature, severity, or duration, or the unexpected incidence of known adverse events
- Obtaining new scientific knowledge that shows that the study is no longer valid or necessary
- Insufficient recruitment of patients
- Unanticipated adverse device effect (UADE) presenting an unreasonable risk to patients (Sponsor may terminate the study immediately)
- Persistent non-compliance with the protocol
- Persistent non-compliance with IRB/EC or regulatory requirements

If the study is discontinued or suspended prematurely, the Sponsor shall promptly inform all clinical investigator(s) / investigational center(s) of the termination or suspension and the reason(s) for this. The IRB/EC shall also be informed promptly and provided with the reason(s) for the termination or suspension by the Sponsor or by the Site PI / investigational center(s). Regulatory authorities and the personal physicians of the patients may also need to be informed if deemed necessary.

## 25.0 SITE CLOSE-OUT

At the time of the site close-out visit, the site monitor or designee will collect all outstanding study documents, ensure that the Investigator's files are accurate and complete, review record retention requirements with the Investigator, make a final accounting of all study supplies, and ensure that all applicable requirements are met for the study. The observations and actions made at this visit will be documented in a final closeout report.

## 26.0 RESPONSIBILITIES

Aerin Medical Inc. is the manufacturer of the Vivaer™ System and the Sponsor of this study. The study Sponsor has the overall responsibility of the study and will work to ensure compliance with the Investigational Plan, elements of Good Clinical Practice: Consolidated Guidance (ICH, April 1996), signed study agreements and 21 CFR 812.2(b), *Abbreviated Requirements*.

The sponsor will be responsible for, but not limited to, conducting the following tasks:

- Select qualified Investigators
- Select qualified monitors and other contract study personnel
- Provide the Investigational Plan and any subsequent amendments
- Sign the protocol
- Provide appropriate information and device training to Investigators and study site staff
- Promptly inform the Investigators and where applicable any regulatory authorities and Ethics Committees, if the study is prematurely terminated or suspended and the reason for the termination or suspension
- Provide protocol initiation training to include review of the Vivaer System instructions for use, the Investigational Plan, CRF completion guidelines, and guidelines for obtaining informed consent

- Coordinate ongoing communication with CRO(s), consultants and study sites to resolve any problems concerning the protocol or data collection. Every effort will be made to ensure compliance with the protocol
- Retain ownership of all clinical data generated in this study, and control the use of the data for purposes of regulatory submissions to the US and other regulatory agencies
- Protect patient confidentiality
- Collect, store and keep secure, at a minimum, the following documents:
  - A current Curriculum Vitae and medical license of each Investigator
  - The name of the institutions where the study will be conducted
  - The IRB/EC opinion and / or approval, in writing, and relevant correspondence
  - Correspondence with authorities (as required)
  - Investigator Agreement
  - CIP Signature Page
  - Appropriate insurance certificates (as necessary)
  - IRB/EC Approved ICF
  - Names / contact information for study monitor(s)
  - Copies of signed and dated CRFs
  - Records of any adverse events and adverse device effects
  - Statistical analyses and underlying supporting data
  - Final report

